### 7.3.2 Accountability

The Investigator or their appointed designee is responsible for ensuring that deliveries of study drug are correctly dispensed and recorded, that the product is handled and stored safely and properly, and that it is only being given to participants in accordance with this protocol.

Sites will keep a current log of drug accountability recording:

- What drug supply was received from the Sponsor
- What drug supply was dispensed to each participant
- What drug supply is current in inventory
- What drug supply was destroyed or returned to the Sponsor for destruction

Note: Drug accountability is the responsibility of the Investigator; a written account will be required for all discrepancies.

The Sponsor’s designated Monitor must verify all accountability records during periodic monitoring visits. Unused and used study drug must be stored on site until such accountability has taken place and authorization is received from the Sponsor or Sponsor’s designee that the study drug may be returned or destroyed.

#### **7.4 Overdose/Toxicity Management**

No specific pharmacologic antagonist or antidote exists for CT1812. Therefore, overdose or clinical toxicity should be managed with supportive care and pharmacologic treatments directed at specific symptoms (i.e. benzodiazepines for agitation or antipyretics for fever).

#### **7.5 Blinding and Randomization**

This is a double-blind, placebo controlled study. Study drug will consist of either of two doses of CT1812 or placebo. The placebo will be identical in appearance to both doses of the active CT1812.

The non-blinded statistician assigned to the trial will generate a list with the appropriate number of 4 digit individual study IDs randomly for each arm, randomly assigned to either CT1812 300 mg, CT1812 100 mg or placebo treatment in a 1:1:1 ratio. Randomization will include stratification on the MMSE score with two strata of 18-22 and 23-26.

Should any participant withdraw from the study prior to study completion, leading to insufficient or uninformative data for analysis, the participant may be replaced, at the sponsor's discretion. This participant will be given the same treatment assignment (by the unblinded statistician) as the withdrawn participant.

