5.2. Randomization and Subject Identification Code

This is a double-blind, placebo-controlled study. Study drug will consist of either of two doses of CT1812 or placebo. The placebo will be identical in appearance to both doses of the active CT1812.

The non-blinded statistician assigned to the trial will generate a list with the appropriate number of 4 digit individual study IDs randomly for each arm, randomly assigned to either CT1812 300 mg, CT1812 100 mg or placebo treatment in a 1:1:1 ratio. Randomization will include a stratification factor for the MMSE score (18-22 or 23-26).

The Randomisation Number will be specified as Rrnnn, where:

- nnn = sequential subject id from 001 to 999,

In the listings presenting the individual data, subjects will be identified by randomization number, with dose of CT1812 as a secondary grouping identifier. The screening number will be shown only on the listing of informed consent data.

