9.3. Efficacy Analysis

The change from baseline in the composite scores and clinical outcomes will be analyzed using a mixed effects model including fixed effects for treatment group (i.e. 300 mg active, 100 mg active, placebo), visit and treatment by visit interaction. In addition, the subject's baseline score will be included as a covariate. For each time point up to and

including 6-months, the treatment differences between 300 mg active and placebo, and 100 mg active and placebo will be estimated from the model. In addition, the low and high CT1812 dosed groups will be pooled and compared with the placebo group. This analysis will be considered the primary analysis.

A separate pooled analysis and analysis by arm will also be performed for time points up to and including the 12-month time point.

Additionally, p-values and corresponding two-sided confidence intervals will be provided. The LS Mean Change from Baseline in ADAS-Cog total scores with 95% CI will be presented graphically by treatment group over time.

In the event that a scale or parameter only has a single post-baseline timepoint, an ANCOVA model will be run in place of the MMRM model without the visit and visit by treatment interaction terms. The ANCOVA model will include a fixed effect for treatment group, and the subject's outcome at baseline as a covariate. For parameters for which there are multiple post-baseline timepoints, ANCOVA models such as that just described above may also be run in addition to the MMRM model at various timepoints.

The change from baseline in the ADAS-Cog (sub) scale total score, total time (in seconds) taken to complete both Trail A and Trail B in the NTB, ADCS-ADL total score, MMSE, CDR-SB, and composite scores will be analysed using the MMRM model described above.

To compare 300 mg active vs placebo and 100 mg vs placebo statistically, observed values for ADCS-CGIC will be analyzed using the MMRM model described earlier without the baseline term. Additionally, frequencies and percentages in the ADCS-CGIC will be summarized by visit. Cochran-Mantel-Haenszel mean score statistics, using rank scores will be used to assess the difference in ADCS-CGIC responses at each visit between the CT1812 dose levels and placebo.

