10. IMAGING OUTCOMES

The change from baseline in the outcome will be compared between the treatment groups using the MMRM or ANCOVA model described in section 9.3.

The pooled analysis and analysis by arm will be performed with data for the composite regions and for the individual exploratory regions collected for points up to and including the 6-month time point. This analysis will be considered the primary analysis.

A separate pooled analysis and analysis by arm will also be performed with data for the composite regions and for the individual exploratory regions at time points up to and including the 12-month time point.

10.1. [¹¹C] UCB-J PET Distribution Volume Ratio (DVR)

For ¹¹C-UCB-J, the primary imaging outcome measure is *DVR* as produced by the Simplified Reference Tissue Model (SRTM2) using dynamic scan data from 0 to 60 min and the whole cerebellum as a reference region. For *DVR*, a composite region will be determined, including: prefrontal, lateral temporal, posterior cingulate/precuneus, anterior cingulate, lateral parietal, medial temporal, and lateral occipital regions. For the ¹¹C-UCB-J DVR outcome composite region the primary model will be analyzed without reference to age and ApoE4 status, however additional models will be run that include age and ApoE4 status as sensitivity analyses. Analyses will also be conducted to assess the relationship of age and ApoE4 status with the dependent DVR variable and to determine if there is any imbalance on these variables between the treatment groups.

Regional analyses will first focus on the hippocampus since the recent cross-sectional study has shown this to be the region of largest group differences in synaptic density when comparing a group of participants with AD to healthy participants.

Individual exploratory regions include:

- Hippocampus
- Entorhinal cortex
- Parahippocampal cortex
- Amygdala
- Fusiform gyrus

- Lingual gyrus
- Inferior/middle temporal cortex
- Anterior cingulum
- Posterior cingulum
- Precuneus
- Prefrontal cortex
- Superior temporal cortex
- Lateral parietal cortex
- Lateral occipital cortex
- Pericentral cortex
- Medial occipital cortex

10.2. [¹⁸F]FDG PET SUV ratio (SUVR)

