11.7. Statistical Analysis of Pharmacodynamic Parameters

Change from baseline in pharmacodynamic endpoints of CSF will be analysed using the MMRM or ANCOVA model described in section 9.3. The analysis will be performed for time points up to and including the 6-month time point, and 12-month time point respectively.

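### Randomisation is stratified by MMSE, but no planned model includes the stratum; if MMSE predicts outcome, the ADCS-CGIC, imaging and CSF comparisons lose power

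*Protocol*

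**What the plan says.** Protocol 7.5: "Randomization will include stratification on the MMSE score with two strata of 18-22 and 23-26". SAP 5.2 restates the factor with the same cut-points.

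The efficacy model in SAP 9.3 is a "mixed effects model including fixed effects for treatment group (i.e. 300 mg active, 100 mg active, placebo), visit and treatment by visit interaction", with the participant's baseline score as covariate. Where an outcome has a single post-baseline time point, the ANCOVA has treatment group and the outcome's baseline. Protocol 17.4 has the same terms and leaves any further covariates to the SAP.

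- **ADCS-CGIC (SAP 9.3):** "observed values for ADCS-CGIC will be analyzed using the MMRM model described earlier without the baseline term". In addition, "Cochran-Mantel-Haenszel mean score statistics, using rank scores will be used to assess the difference in ADCS-CGIC responses at each visit". No stratification variable is named for that test.
- **Imaging (SAP 10):** change from baseline "will be compared between the treatment groups using the MMRM or ANCOVA model described in section 9.3". For the DVR composite region, "additional models will be run that include age and ApoE4 status as sensitivity analyses".
- **CSF biomarkers (SAP 11.7):** "Change from baseline in pharmacodynamic endpoints of CSF will be analysed using the MMRM or ANCOVA model described in section 9.3".

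SAP 9.4 mentions age, gender, education and ApoE as possible further explorations, but not MMSE. SAP 11.8 reports no departure from the protocol's analysis. The MMSE stratum appears in no model, and its absence is not explained.

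**The concern.** Stratifying by MMSE implies that the sponsor thought disease severity worth balancing. If it is prognostic, balancing it by design and then omitting it from the model has two effects. The between-stratum variance goes into the residual, so power is lost. Where the arms really are balanced within strata, the reported standard error is also larger than the true sampling variability, so the test is mildly conservative.

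Exposure differs by endpoint. ADCS-CGIC has most to lose, because its model holds no measure of severity at all. Imaging and CSF models hold only their own baselines. ADAS-Cog and the cognitive composites are less exposed, since their baselines probably carry much of the same information. The MMSE endpoint is not exposed: SAP 9.1 schedules MMSE at screening and not at Day 1, so its baseline covariate is the screening score.

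With about seven participants per arm and a stated power of about 68% (one-sided) for the main imaging comparison, there is little precision to spare.

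**Working it through.** **1. The plan's own figure.** Protocol 17.5 and SAP 4.5 assume a 30% synapse loss with one third restored, no placebo change, and 10% variability at each scan.

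- Effect: from 70 to 80, or 10/70 = 14.3% of baseline.
- SD of change, taking the two scan errors as independent (assumption): 10 × √2 = 14.14%.
- Standardised effect: 14.3/14.14 = 1.01.
- Noncentrality, 14 v 7: 1.01 × √(14 × 7/21) = 1.01 × 2.160 = 2.18, on 19 df.
- Power, one-sided 5%: 67.7%, which reproduces the stated 68%. Two-sided, as in the intervals SAP 9.3 calls for: 54.4%.

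**2. Size of the omitted term.** The documents give no MMSE-outcome relation, so a range is assumed. With strata of 12 and 9 (assumed) and a stratum difference of *d* residual SDs:

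share of variance = 0.245*d*² / (1 + 0.245*d*²), where 0.245 = (12/21)(9/21).

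For *d* = 0, 0.5 and 1.0 the share is 0%, 6% and 20%.

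**3. Power without v with the stratum (%).** Assumed: N = 21, true effect 1.0 residual SD, two-sided 5%, one time point, complete data. Settings (a) to (d) compare pooled doses with placebo in a linear model with two dose indicators, 10,000 trials each (Monte Carlo error about 0.5 point). The outcome's baseline has coefficient 0.3 and is omitted in (d). Setting (e) compares one dose with placebo, 6,000 trials, with a latent normal cut into seven categories at −2, −1.2, −0.5, 0.5, 1.2 and 2 (assumed).

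| Setting | *d* = 0 | *d* = 0.5 | *d* = 1.0 |
|---|---|---|---|
| (a) Blocks of 3, baseline unrelated to stratum | 50.8 v 50.2 | 47.5 v 50.2 | 40.1 v 50.0 |
| (b) As (a), baseline correlated 0.6 with stratum | 51.7 v 50.2 | 49.5 v 50.2 | 45.0 v 50.0 |
| (c) No within-stratum balance, baseline unrelated | 50.1 v 47.8 | 47.7 v 47.8 | 41.9 v 48.2 |
| (d) No baseline term (ADCS-CGIC type), blocks of 3 | 53.3 v 52.9 | 50.7 v 52.9 | 42.5 v 52.6 |
| (e) Rank-score CMH, 7 v 7 | 37.7 v 35.9 | 34.7 v 35.1 | 27.3 v 34.5 |

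At *d* = 1.0 the gains are 9.9, 5.0, 6.3, 10.1 and 7.2 points. At *d* = 0 the costs are 0.6, 1.5, 2.3, 0.4 and 1.8 points. Blocks of 6 give the same pattern as (a). Repeat simulations of these settings agree within about 2.6 points.

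**4. Direction of the error.** In (a), type I error without the stratum is 4.9, 4.2 and 2.9% across the three columns. At *d* = 1.0 the mean reported standard error is 0.533 against a true 0.479, about 11% too wide (0.533/0.479 = 1.11); with the stratum it is 0.470 against 0.476. In (c), type I error is 4.6 to 4.9%, so without within-stratum balance the test is not materially conservative.

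**5. Cross-check on the plan's effect size.** Here the standardised effect is 1.01, the total SD is held fixed, there is no baseline covariate, and blocks of 3 are used. Pooled two-sided power without v with the stratum is 54.6 v 54.3 at a 0% share, 54.1 v 58.5 at 10%, 53.7 v 64.1 at 20% and 52.9 v 70.1 at 30%. The analytic check for the adjusted model at 20% (noncentrality 1.01/√0.8 × 2.160 = 2.44, 17 df) gives 63.3%.

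**The case against.** The harm is conditional, and nothing in the documents supports the condition. For DVR, the planning model assumes no placebo change, and its 10% variability rests on test-retest reliability. A stratum cannot explain scan noise, so the plan's only variance information points towards no loss. At *d* = 0.5 the gain is 2.7, 0.7, 0.1, 2.2 and 0.4 points in settings (a) to (e), so three of the five show almost none. Balance is also uncertain: no block size is stated, and under Protocol 7.5 a replacement takes the withdrawn participant's treatment with no stated stratum match. If there is no within-stratum balance and baseline correlates 0.6 with the stratum, adding the term loses power at *d* = 0 (50.3 to 48.0) and at 0.5 (49.9 to 48.8), and gains 3.4 points only at 1.0. The simulations use one time point, whereas ADCS-CGIC and DVR are measured at several visits. The Cochran-Mantel-Haenszel point is drawn from silence. All affected endpoints are secondary or exploratory in a pilot.

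Most of this stands as a limit on size. The larger gains need a strong stratum effect, the multi-visit model was not simulated, and the case is weakest for ADAS-Cog and the composites. None of it shows that the plan uses the stratum or explains leaving it out. The planning model is a simplification for sample size and says nothing about ADCS-CGIC or CSF. Leaving the choice until later has its own cost, because SAP 1 classes analyses added after review of unblinded results as post hoc.

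**Conclusion.** The concern holds. Randomisation uses the MMSE stratum, no specified analysis does, and no reason is given. In the main simulations the power lost runs from nil to about 10 points as the stratum's share of residual variance goes from 0 to 20%. A 30% share would cost about 17 points in a model with no baseline covariate (70.1 − 52.9), but nothing in the documents supports a share that large.

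The range rests on assumed effect size, stratum sizes, block structure and MMSE-outcome relation, with a single complete time point. The consequence is lost precision and, where within-stratum balance is achieved, a mildly conservative test. It does not produce false positives, and the primary safety objective is unaffected. The change is worth making because it is simple, but the trial's validity does not depend on it.

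**What to change.** In SAP 9.3, which SAP 10 and 11.7 apply by reference:

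- Add the randomisation MMSE stratum (18-22 / 23-26), or continuous screening MMSE, as a covariate in the MMRM and ANCOVA models. ADCS-CGIC, imaging and CSF outcomes have most to gain.
- Leave it out for the MMSE endpoint, whose baseline is already in the model.
- State that the ADCS-CGIC Cochran-Mantel-Haenszel test is stratified by the same factor.
- If the unadjusted models are kept, give the reason.

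Settle this before unblinding. The cost is one term already recorded for randomisation and one degree of freedom. If the stratum is uninformative, the power given up is about 0.5 point with balanced blocks, 1.5 if the outcome's baseline correlates 0.6 with the stratum, 2.3 without within-stratum balance, and 1.8 for the 7 v 7 rank test.

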### **8 INVESTIGATORS, SITES AND DURATION**

#### **8.1 Investigator and Site**

This single-center trial will be conducted at [REDACTED]

#### **8.2 Duration of Study**

Each participant and caregiver will participate in a screening period of up to 60 days, followed by the primary double-blind treatment period of 24 weeks (169 days +/-2) followed by an optional double-blind extension treatment period of another 24 weeks (337 days +/-2). A follow up visit will occur 2 weeks after the last day of dosing. Including the screening period, the total duration of participant participation in the study is up to 36 week for the primary study or up to 60 weeks for the extension study. If a delay occurs with subjects progressing from the primary study to the extension study, a maximum of 4 weeks will be permitted.

### **8.3 Termination of Study**

This study may be terminated at the discretion of the Sponsor. Occurrence of the stopping rules defined in Section 7.3.1 may result in early termination of the study.

## **9 STUDY POPULATION**

### **9.1 Number of Participants**

Up to 21 participants will be randomized. A maximum of 25 participants may receive study drugs and PET tracers, if replacement of drop-outs occurs.

### **9.2 Inclusion Criteria**

Participants may be included in the study only if they meet all of the following criteria:

- 1) Men, and women of non-childbearing potential, 50-85 years of age inclusively, with a diagnosis of mild to moderate Alzheimer's disease according to the 2011 National Institute on Aging – Alzheimer's Association criteria (McKhann et al, 2011) and at least a 6 month decline in cognitive function documented in the medical record.
  - a) Non-childbearing potential for women is defined as postmenopausal [last natural menses greater than 24 months; in women under age 55, menopausal status will be documented with serum follicle stimulating hormone (FSH) test] or undergone a documented bilateral tubal ligation or hysterectomy.
  - b) Male participants who are sexually active with a woman of child-bearing potential must agree to use condoms during the trial and for 3 months after last dose unless the woman is using an acceptable means of birth control. Acceptable forms of birth control include abstinence, birth control pills, or any double combination of: intrauterine device (IUD), male or female condom, diaphragm, sponge, and cervical cap.
- 2) Neuroimaging (MRI) obtained during screening consistent with the clinical diagnosis of Alzheimer's disease and without findings of significant exclusionary abnormalities (see exclusion criteria, number 3).
- 3) MMSE 18-26 inclusive.
- 4) A positive amyloid (e.g., Pittsburgh imaging compound B) scan at screening, or history of a positive amyloid scan prior to study entry, or prior lumbar puncture with a CSF A $\beta$  concentration consistent with Alzheimer's disease.

- 5) Formal education of eight or more years.
- 6) Must have a caregiver who sees them at least 10 hours per week, oversees the administration of study drug, and is willing and able to oversee administration of study medication and participate in all clinic visits and some study assessments. The caregiver must provide written informed consent to participate in the study.
- 7) Living at home or in the community (assisted living acceptable).
- 8) Able to swallow CT1812 capsules.
- 9) Stable pharmacological treatment of any other chronic conditions for at least 30 days prior to screening.
- 10) Capable of providing either written informed consent or oral assent to the study procedures and for use of protected health information (Health Insurance Portability and Accountability Act [HIPAA] Authorization, if applicable). If the Participant can provide only assent, their legally authorized representative also must provide written informed consent. Written informed consent also shall be obtained from the responsible caregiver. All consent processes must be undertaken in the presence of a witness and prior to any study procedures.
- 11) Must consent to apolipoprotein E (ApoE) genotyping.
- 12) Generally healthy with mobility (ambulatory or ambulatory-aided, i.e., walker or cane), vision and hearing (hearing aid permissible) sufficient for compliance with testing procedures.
- 13) Able to complete all screening evaluations.

### **9.3 Exclusion Criteria**

Participants will be excluded from the study if any of the following conditions apply:

- 1) Hospitalization or change of chronic concomitant medication within one month prior to screening.
- 2) Patients living in a continuous care nursing facility.
- 3) Screening MRI of the brain indicative of significant abnormality, including, but not limited to, prior hemorrhage or infarct  $>1 \text{ cm}^3$ ,  $>3$  lacunar infarcts, cerebral contusion, encephalomalacia, aneurysm, vascular malformation, subdural hematoma, hydrocephalus, space-occupying lesion (e.g. abscess or brain tumor such as meningioma).

- 4) MRI incompatible implants and other contraindications for MRI, such as pacemaker, artificial joints, non-removable body piercings, etc. Additionally, participants who meet the following imaging exclusion criteria will not be included in this study:
  - a. Claustrophobia that will result in significant anxiety and difficulty lying still for brain imaging (MRI or PET).
  - b. Participation in other research studies involving ionizing radiation within one year of the PET scans that would cause the participant to exceed the yearly dose limits for healthy volunteers.
  - c. History of IV drug use that would prevent venous access for PET tracer injection.
  - d. Severe motor problems that prevent the participant from lying still for brain imaging.
  - e. Severe chronic pain (e.g., as the result of rheumatoid arthritis) that would prevent them from lying still during brain imaging.
- 5) Clinical or laboratory findings consistent with:
  - a) Other primary degenerative dementia, (dementia with Lewy bodies, fronto-temporal dementia, Huntington's disease, Jacob-Creutzfeld Disease, Down's syndrome, etc.).
  - b) Other neurodegenerative condition (Parkinson's disease, amyotrophic lateral sclerosis, etc.)
  - c) Seizure disorder
  - d) Other infectious, metabolic or systemic diseases affecting the central nervous system (syphilis, present hypothyroidism, present vitamin B12 or folate deficiency, other laboratory values) etc.)
- 6) A current Diagnostic and Statistical Manual of Mental Disorders-V (DSM-V) diagnosis of active major depression, schizophrenia or bipolar disorder. Patients with depressive symptoms successfully managed by a stable dose of an antidepressant are allowed entry.
- 7) Clinically significant, advanced or unstable disease that may interfere with outcome evaluations, such as:
  - a) Chronic liver disease, liver function test abnormalities or other signs of hepatic insufficiency (ALT, AST, total bilirubin > 1.5 x ULN)
  - b) Respiratory insufficiency

- c) Renal insufficiency defined as eGFR <45 mL/min based on the CKD-EPI formula,  

- d) Heart disease (myocardial infarction, unstable angina, heart failure, cardiomyopathy within six months before screening)
- e) Bradycardia (<45/min.) or tachycardia (>100/min.)
- f) Poorly managed hypertension (systolic >160 mm Hg and/or diastolic >95 mm Hg) or hypotension (systolic <90 mm Hg and/or diastolic <60 mm Hg)
- g) Uncontrolled diabetes defined by glycosylated hemoglobin (HbA1c) >7.5%
- 8) History of cancer within 3 years of screening with the exception of fully excised non-melanoma skin cancers or non-metastatic prostate cancer that has been stable for at least 6 months.
- 9) Seropositive for human immunodeficiency virus (HIV).
- 10) History of acute/chronic hepatitis B or C and/or carriers of hepatitis B (seropositive for Hepatitis B surface antigen [HbsAg] or anti-Hepatitis C [HCV] antibody).
- 11) Clinically significant abnormalities in screening laboratory tests, including:
  - a) hematocrit less than 33% for males and less than 30% for females
  - b) absolute neutrophil cell count of 1200/uL (with the exception of a documented history of a chronic benign neutropenia), or platelet cell count of <120,000/uL
  - c) INR >1.4 or other coagulopathy, confirmed by repeat.
- 12) Disability that may prevent the patient from completing all study requirements (e.g. blindness, deafness, severe language difficulty, etc.).
- 13) Women who are fertile and of childbearing potential.
- 14) Within 4 weeks of screening visit or during the course of the study, concurrent treatment with antipsychotic agents (except risperidone  $\leq 1.5$  mg/day, quetiapine  $\leq 100$  mg/day, olanzapine  $\leq 5$  mg/day, and aripiprazole  $\leq 10$  mg/day), antiepileptics (except lamotrigine, gabapentin and pregabalin for nonseizure indications), centrally active anti-hypertensive drugs (e.g., clonidine, l-methyl dopa, guanidine, guanfacine, etc.), opiate analgesics, systemic corticosteroids, psychostimulants, antiparkinsonian medications (except for non-parkinsonian indications) and mood stabilizers (e.g., valproate, lithium), sedatives and anxiolytics with the exception that use of short- to medium-acting benzodiazepines for treatment of insomnia is permitted,

however, use of sedatives or hypnotics should be avoided for 8 hours before administration of cognitive tests. See Appendix A and B for a representative list.

- 15) Any disorder that could interfere with the absorption, distribution, metabolism or excretion of drugs (e.g. small bowel disease, Crohn's disease, celiac disease, or liver disease).
- 16) Nootropic drugs except stable AD meds (acetylcholinesterase inhibitors and memantine).
- 17) Suspected or known drug or alcohol abuse, i.e. more than approximately 60 g alcohol (approximately 1 liter of beer or 0.5 liter of wine) per day indicated by elevated MCV significantly above normal value at screening.
- 18) Suspected or known allergy to any components of the study treatments.
- 19) Enrollment in another investigational study or intake of investigational drug within the previous 30 days or five half lives of the investigational drug, whichever is longer.
- 20) Previous exposure to anti A $\beta$  vaccines.
- 21) Exposure to passive immunotherapies for AD (e.g. monoclonal antibodies) within the previous 180 days to dosing, and BACE inhibitors within the previous 30 days to dosing.
- 22) Contraindication to undergoing an LP including, but not limited to: inability to tolerate an appropriately flexed position for the time necessary to perform an LP; INR > 1.4 or other coagulopathy; platelet count of < 120,000/ $\mu$ L; infection at the desired lumbar puncture site; taking anti-coagulant medication within 90 days of screening (Note: low dose aspirin is permitted); degenerative arthritis of the lumbar spine; suspected non-communicating hydrocephalus or intracranial mass; prior history of spinal mass or trauma.
- 23) Use of NSAIDs more than 2 days in within any 7 day period. Each incidence of use must be recorded in the source and Case Report Form (CRF).
- 24) Any condition, which in the opinion of the investigator or the sponsor makes the patient unsuitable for inclusion.
- 25) Intake of drugs or substances potentially involved in clinically significant CYP3A4 inhibition or induction or P-gp mediated drug interactions with CT1812, within 4 weeks or five half-lives of the interacting drug prior to administration of CT1812 and throughout the course of the study. Grapefruit juice should be avoided in the two weeks prior to dosing. See Appendix A and B for a list of these prohibited substances.

